Study Design: This will be a 6-month (with follow-up, if necessary, to monitor residual implant), open-label, multicenter, adaptive study evaluating the safety, tolerability, and efficacy of 2 formulations of dexamethasone intravitreal implant, AR-1105, in a single eye of up-to 45 subjects between 18 and 80 years of age with macular edema (ME) secondary to retinal vein occlusion (RVO). Since this study represents the first-in-human experience with AR-1105, the study will begin with an initial phase, during which time, up to a maximum of 5 subjects will be treated with AR-1105 clinical formulation 1 (AR-1105-CF1) and followed during weekly visits for up to 2 weeks post-treatment to assess tolerability and safety. Providing none of the subjects experience any clinically-meaningful ocular adverse reactions (possibly) related to treatment with AR-1105 during the initial phase, the study will continue into the randomized phase. During the randomized phase of the study, subjects will be assigned in a 1:1 ratio to either AR-1105-CF1 or AR-1105 clinical formulation 2 (AR-1105-CF2). Data collected from the subjects enrolled into the randomized phase of the study will be primarily summarized separately from subjects enrolled during the initial phase. Treatment will consist of a single intravitreal administration with AR-1105-CF1 or -CF2, each of which has a target dose of 340 µg dexamethasone (2 implants, single injection). During the randomized phase, each treatment group will enroll approximately 20 subjects (i.e. in addition to the enrolled subjects who will participate in the initial phase on AR-1105-CF1). An interim analysis of the first 20 subjects randomized to CF1 or CF2 may be conducted when they have completed 6 months post-treatment to assist in planning future studies. When all subjects in each treatment group have completed their Month 6 visit, the primary safety and efficacy analyses will be conducted. Data collected through Month 6 on the safety and tolerability of each formulation, as well as efficacy signals for each subject randomized, will be used to determine which formulation will be selected for further clinical development. Any subject who presents at Month 6 with visible residual implant will be followed until they require retreatment (following the criteria provided for rescue therapy), or until 1 month after the implant is no longer visible or to Month 9, whichever occurs first. Rescue therapy in the form of standard of care, will be offered to any subject who, in the opinion of the investigator, requires additional therapy for their RVO due to lack of efficacy after Month 3/Week 12. Minimum guideline criteria for considering rescue are an increase in CRT of 50 µm and decrease in BCVA of ≥ 7 letters at any time compared to baseline. In the case of elevated intraocular pressure (IOP) or cataract, investigators should treat the subject according to standard practice. In the case of a cataract, removal should be performed as soon as possible since BCVA could be impacted by the cataract.

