Within the last 10 years, intravitreal pharmacotherapy has revolutionized the therapeutic options for ME-associated retinal vascular diseases, and particularly for RVO. Current options for treating ME depend upon the cause and severity of the condition. In the case of RVO, the goal is to reduce the amount of fluid leakage and decrease the edema, thus leading to improved visual acuity (VA). Argon laser photocoagulation was used for many years to treat ME associated with BRVO, but was less effective in the treatment of CRVO, and was not successful in all patients ([Fekrat 1997](#)). Currently, two classes of medication are approved to treat ME following RVO – corticosteroids (such as OZURDEX® dexamethasone intravitreal implant), and more recently, anti-vascular endothelial growth factor (VEGF) therapies such as ranibizumab (LUCENTIS®) and afibbercept (EYLEA®). The anti-VEGFs, while effective at modulating vascular permeability, do not address the inflammatory component of RVO however. Corticosteroids have the advantage of targeting the three components of the pathophysiology of RVO; reducing ME through inhibition of multiple inflammatory mediators, stabilizing the blood brain barrier and decreasing vascular permeability ([Zas 2017](#), [OZURDEX PI](#)). Corticosteroids such as dexamethasone (OZURDEX) and triamcinolone (KENALOG®) have demonstrated ME reduction and improvement in VA when dosed intravitreally ([Cekic 2005](#), [Ip 2003](#), [OZURDEX PI](#)). OZURDEX (0.7 mg dexamethasone) intravitreal implant has been evaluated in RVO and demonstrated efficacy up to 6 months ([Haller 2010](#)), although the peak efficacy is generally achieved by Month 3 ([Joshi 2013](#), [Bandello 2015](#)).

While both classes of medication have demonstrated efficacy in RVO patients, the treatment burden is high, with the anti-VEGFs typically requiring monthly ([LUCENTIS PI](#), [EYLEA PI](#)) intravitreal injections, and the dexamethasone intravitreal implant typically requiring re-injection every 3 months ([Bezatis 2013](#), [Augustin 2014](#)). A corticosteroid implant that offered a longer duration of effect would provide the benefit of reducing the

treatment burden on patients while treating the inflammatory components of ME that are not addressed by inhibition of VEGF.

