4. STUDY POPULATION SELECTION

4.1 Study Population

4.2 Inclusion Criteria

Subjects MUST meet all of the following criteria at the screening and baseline visits to enter into the study:

1. At least 18 years of age
2. Vision-loss attributed to clinically detectable ME associated with either CRVO or BRVO. Subjects may be treatment-naïve, or if previously-treated with a steroid, must have demonstrated response to treatment.
3. Duration of ME (defined as the time since initial diagnosis of ME) ≥ 9 months in subjects with CRVO and ≥ 12 months in subjects with BRVO. If both eyes are eligible, the study eye will be the eye with worse VA
4. Best-corrected visual acuity (BCVA) as measured by the ETDRS methodology of between 25 and 70 letters (+1.2 and +0.3 logMAR units or 20/320 and 20/40 Snellen equivalent) in the study eye
5. Retinal thickness in the central subfield (as measured by SD-OCT) of >290 μm (females) and >305 μm (males) if using a Cirrus (Zeiss) instrument, or if a Spectralis (Heidelberg) instrument is used, thickness should be >305 μm (females) or >320 μm (males) in the study eye
6. Be able to understand and willing to provide written informed consent
7. Be willing and able to adhere to the instructions set forth in the study protocol

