5.4 Method of Assigning Patients to Treatment Groups

Subjects will be assigned to treatment groups through the use of an interactive response technology (IRT) system. [REDACTED]

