9.4 Demographics and Baseline Characteristics

Demographic and baseline characteristics such as age, gender, race, and ethnicity will be summarized and listed. Medical history, history of ocular surgery and procedures, and RVO history will also be summarized and listed.

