4.1 Method of Assigning Subjects to Treatment Groups

Providing none of the subjects experience any clinically-meaningful ocular adverse reactions (possibly) related to treatment with AR-1105 during the initial phase, the study will continue into the randomized phase. During the randomized phase of the study, subjects will be assigned in a 1:1 ratio to either AR-1105-CF1 or AR-1105-CF2.

5. Sample Size and Power Considerations

This study is not powered to detect a pre-stated efficacy signal, but rather will be used to inform the design and power for future studies. With a sample size of 20 evaluable subjects per treatment group, the study will have 95% confidence of ruling out adverse events (AE) with true incidence rates of 13.9% or higher within each treatment group. That is, with 20 subjects in a treatment group, if an AE of a specific type is not observed, then with 95% confidence, the true incidence rate of that AE is less than 13.9%.

6. Data Preparation

All reported study data will be recorded on the electronic case report forms (eCRF) supplied by Statistic & Data Corporation (SDC). Only the Principal Investigator and authorized study staff according to the Delegation of Responsibilities log are entitled to make entries in the eCRF.

After data are entered into the clinical study database, electronic edit checks and data review will be performed. All data validation specifications and procedures are detailed in the Data Validation Manual as a separate document. When the database has been declared to be complete and accurate, the database will be locked. Any changes to the database after data have been locked can only be made with the approval of the Sponsor and Trial Runners in consultation with SDC.

The final analyses outlined in this document will be carried out after the following have occurred:

- All data management requirements are met according to SDC standard operating procedures, including data entry, performance of edit and validation checks, documentation and resolution of data queries, and database lock with written authorization provided by appropriate SDC and Sponsor personnel.
- Protocol deviations have been identified and status defined (major/minor deviations).
- Analysis populations have been determined.

7. Analysis Populations

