8.4 Data Analysis Conventions

All data analyses will be performed by SDC. Statistical programming and analyses will be performed using SAS® Version 9.4 or higher. Output will be provided in rich text format (RTF) for tables and portable document format (PDF) for tables, listings, and figures using landscape orientation. All study data will be listed by treatment (and phase [initial vs randomized] for CF1), subject and visit (as applicable).

Summaries for continuous and ordinal variables will include the number of observations (n), arithmetic mean, standard deviation (SD), median, minimum, and maximum. Minima and maxima will be reported with the same precision as the raw values; means and medians will be presented to one additional decimal place than reported in the raw values. Standard deviations will be presented to two additional decimal places than reported in the raw values. Summaries for discrete variables will include number and percentages. All percentages will be rounded to one decimal place (i.e., XX.X%). Change from baseline will be calculated as follow-up visit minus baseline.

All statistical tests will be two-sided with a significance level of 0.05 ($\alpha = 0.05$) unless otherwise specified. Confidence intervals for differences between treatment groups will be two-sided at 90% and 95% confidence. All p-values will be rounded to four decimal places; p-values less than 0.0001 will be presented as "<0.0001"; p-values greater than 0.9999 will be presented as ">0.9999."

Unless otherwise specified, summaries will be presented by treatment group and, where appropriate, visit.

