A linear model with change from baseline BCVA letters for study eye only as the response, baseline BCVA letters as a covariate, and treatment group as a main effect will be fit to determine treatment group effect with separate models completed for each follow-up visit. These analyses will be used to determine differences in formulations and may be used to assess whether there are differences in outcomes between subjects' data pre- and post-interim to determine whether the data may be pooled. Subjects who receive rescue medication prior to the summarized visit will have their measure replaced with their last observation prior to receiving rescue medication. The least squares mean, standard error, and CI for each treatment group, and the difference between treatment groups will be presented for

study eye only. Additionally, analyses will be completed using individual two-sample t-tests and 90% and 95% CIs around the difference between treatment groups in mean BCVA and mean change from baseline BCVA for study eye only.

Median time (in months) to achieve a treatment response of ≥ 15 letters improvement from baseline in BCVA for study eye and median time (in months) to rescue therapy will be estimated using Kaplan-Meier methods with 90% and 95% CI, calculated using the method of Brookmeyer and Crowley (1982). The log rank statistic will be used to determine differences in time to achieve response between the two treatment groups to determine differences in formulations. Cox proportional hazards will also be used to analyze time to event, including baseline BCVA as a covariate. Results from unscheduled visits or early termination visits will be included in the time to event analysis.

For the event of achieving a treatment response of ≥ 15 letters improvement from baseline in BCVA for study eye, the starting date will be the date of first dose. Subjects receiving rescue medications prior to or on the same date as the achievement of improvement will be considered censored on the day of rescue medication receipt; subjects with neither rescue medications received nor improvement achieved will be considered censored on the last date known to be rescue medication free and improvement achievement free. For the event of receiving rescue therapy, the starting date for the time to event evaluation will be the date of first dose. Subjects who do not receive rescue therapy will be considered censored on the last date known to be event free.

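### RVO type (BRVO or CRVO) is known for every subject at entry but enters no efficacy model and no listed SAP table; add it to the linear models and tabulate it by arm

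*SAP*

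**What the plan says.** **Population.** Protocol 4.2 admits subjects with "ME associated with either CRVO or BRVO". It sets the minimum duration of macular edema by type: 9 months for CRVO and 12 months for BRVO. Eligibility therefore cannot be checked without classifying each subject.

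**Allocation.** SAP 4.1 says that "subjects will be assigned in a 1:1 ratio to either AR-1105-CF1 or AR-1105-CF2". The Protocol synopsis says that in the randomized phase "each treatment group will enroll approximately 20 subjects". Protocol 5.4 says "Subjects will be assigned to treatment groups through the use of an interactive response technology (IRT) system", and the text after that sentence is redacted.

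**Efficacy models.** The SAP 13.1 linear model for BCVA change has "baseline BCVA letters as a covariate, and treatment group as a main effect will be fit to determine treatment group effect", fitted separately at each follow-up visit. The exact logistic model and the Cox model also contain only treatment and baseline BCVA. Fisher's exact test, the Farrington-Manning intervals, the t-tests and the log-rank test use no baseline factor. SAP 13.2 applies the same approaches to CRT.

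**Baseline description.** Protocol 9.4 says that "RVO history will also be summarized and listed". SAP 10.1 names only age, gender, race and ethnicity. SAP 20 lists no RVO-history table, and SAP 17 does not record this as a change from the protocol. The ocular medical history table might show RVO as a coded term, but nothing says that it would separate the two types.

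**Use.** The synopsis says that safety, tolerability and efficacy signals through Month 6 will inform which formulation goes forward.

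**The concern.** The trial enrols two forms of the disease and compares two formulations with about 20 subjects each. If the forms differ in visual or anatomical outcome, an uneven split between arms moves the estimated formulation difference by the imbalance times the outcome gap. The planned models cannot remove that movement, except for the part that acts through baseline BCVA. The listed tables would not clearly show a reader that the split was uneven.

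The comparison feeds the choice of formulation, and the classification is already in hand. Leaving it out gives up a small, nearly free improvement. If the redacted text does stratify by type, the models then omit a stratification factor, and their standard errors give no credit for the balance it achieved.

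**Working it through.** **The plan's own figure.** The only sample-size figure is the 13.9% bound for an adverse event not seen in 20 subjects: 1 − 0.05^(1/20) = 0.1391. It reproduces and does not depend on the efficacy model. There is no efficacy power calculation to reproduce.

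**Inputs from the documents.** 20 per arm, 40 randomized, 1:1; model terms as in SAP 13.1.

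**Assumptions (the documents give no values).**
- No stratification by RVO type
- 12, 16 or 20 CRVO subjects among 40 (30-50%)
- Outcome gap between types of 3-8 letters
- Within-type SD of 10-15 letters
- RVO type explains 5-10% of outcome variance

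**1. Chance of imbalance.** With K CRVO subjects among 40, the number k in one arm is hypergeometric: P(k) = C(K,k)·C(40−K,20−k)/C(40,20). The arms differ by |2k − K| subjects.

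| CRVO among 40 | Differ by ≥4 (20 points) | Differ by ≥6 (30 points) |
|---|---|---|
| 12 | 0.301 | 0.082 |
| 16 | 0.333 | 0.105 |
| 20 | 0.343 | 0.113 |

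An even total allows only even differences. For odd totals from 13 to 19, a difference of 4 or more means at least 5, and the same formula gives 0.18-0.21. Without fixing the total (two independent binomials, CRVO share 30-50%), a 20-point imbalance has probability 0.23-0.27 and a 30-point imbalance 0.06-0.08. So 30-34% is the upper part of the plausible range.

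**2. Shift in the BCVA difference** = imbalance × gap.
- 20 points: 0.20 × 3 = 0.6 letters to 0.20 × 8 = 1.6 letters
- 30 points: 0.30 × 3 = 0.9 letters to 0.30 × 8 = 2.4 letters

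**3. Against the standard error.** SE = SD × √(2/20): 10 × 0.316 = 3.16 and 15 × 0.316 = 4.74 letters. The 20-point shift is 0.6/4.74 = 0.13 SE to 1.6/3.16 = 0.51 SE. Even a 30-point imbalance with a 10-letter gap gives 3.0/3.16 = 0.95 SE.

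**4. Responder rate.** For an assumed 10-20 point gap between types, a 20-point imbalance shifts the 15-letter responder difference by 0.20 × 10 = 2 to 0.20 × 20 = 4 points. One subject in 20 is 5 points.

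**5. Net gain from adjusting.** Residual degrees of freedom go from 40 − 3 = 37 to 36. The gross SE ratio is √(1 − R²): 0.975 at R² = 5% and 0.949 at 10%. Estimating the extra term also inflates the variance by 1/(1 − r²), where r is the treatment-type correlation. Under simple allocation the expected r² is 1/39.
- R² = 5%: √(0.95 × 39/38) = 0.987, a net reduction of 1.3%
- R² = 10%: √(0.90 × 39/38) = 0.961, a net reduction of 3.9%

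At exactly a 20-point imbalance, r² = 0.01/(s(1 − s)) for CRVO share s, or 0.040-0.048. The net reduction is then about 0.1-0.5% (R² = 5%) or about 3% (R² = 10%). Where imbalance is present, the benefit is mainly removal of the shift.

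**The case against.** **Stratification may exist.** The redaction falls where a stratification factor would be named, and with stratification the shifts above are close to zero. This stands, so the imbalance figures are conditional. The recommendation is not, because a stratification factor belongs in the model too.

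**The planned intervals are valid as they are.** Under randomisation their coverage already allows for chance imbalance, and any part of the type effect that runs through baseline BCVA is adjusted. This stands. The point concerns precision and interpretation in the trial actually observed.

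**The plan hardly separates the types.** Objectives, dose, rescue guideline, endpoints and the 315 µm resolution cut-off are common to both. Only the duration threshold differs. A reader might infer a type difference from the Protocol Introduction, where a treatment "was less effective in the treatment of CRVO". That sentence is about argon laser photocoagulation. It says nothing about response to a steroid, and the documents give no outcome gap by type.

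**Other covariates have a claim.** ME duration, prior treatment and OCT instrument could also be argued for, and one prespecified covariate at 20 per arm is defensible. This stands in part. RVO type has the stronger case because it is named in the primary objective and settled at entry for every subject.

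**Adjustment does not reach the first listed endpoint or suit the Cox models.** The 15-letter comparison would remain unadjusted for type. The precision argument does not carry over to Cox models, and the loss-of-resolution analysis in SAP 13.2 uses a responder subset that may have few events. Both stand and limit the fix.

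**Efficacy is secondary.** The study is stated to be unpowered for efficacy, and no p-value rule governs formulation choice. This lowers the priority but does not remove the point.

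**Conclusion.** The omission is certain: RVO type is settled at entry, appears in no efficacy model, and has no listed SAP table despite the Protocol 9.4 commitment on RVO history. Its effect is modest and rests on assumptions. If allocation was not stratified and 12, 16 or 20 of 40 subjects have CRVO, a 20-point imbalance arises in about 30-34% of trials, and less often if the total is odd or not fixed. With a 3-8 letter gap it moves the BCVA difference by 0.6-1.6 letters, about 0.1-0.5 SE for SDs of 10-15 letters.

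A reader might infer that imbalance is likely and certain to go uncorrected, or that the trial's conclusions are biased. The documents do not support this. A 20-point imbalance is less likely than not, stratification is unknown because of the redaction, and the size of any type effect is not given. Priority is low to moderate.

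**What to change.** 1. **Linear models (SAP 13.1 and 13.2).** Add RVO type, as classified for eligibility, as a fixed factor in the BCVA and CRT change-from-baseline models. If randomisation was stratified by type, say so and cite it as the reason.
2. **Baseline table (SAP 10 and 20).** Tabulate RVO type by arm, with the RVO history that Protocol 9.4 promises.
3. **Descriptive results by type.** Show 15-letter responders and numbers rescued by type within arm, without tests. The rescue counts can sit with the time-to-rescue table, since SAP 17 withdraws the separate discrete rescue summary.
4. **Cox models.** Use RVO type only as a sensitivity analysis where events allow. Leave the exact logistic model unchanged, because conditioning on near-continuous baseline BCVA with 40 subjects already leaves a thin reference set.

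The cost is SAP wording, one baseline table, some added rows and one residual degree of freedom. No new data are needed. The trial is open-label and may have an interim review, so the change should be written in before outcomes by arm are examined. If they have already been seen, report the adjusted model as a supplementary analysis, which SAP 1 allows if it is identified in the study report.

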Example SAS codes: PROC LIFETEST Data=xxx method=KM;

Strata treatment/test=logrank;

Time AVAL*CENSOR(0);

Run;

where CENSOR indicates censored subjects.

PROC PHREG Data = xxx;

Class Treatment (param=ref ref='CF2');

model AVAL*CENSOR(0) = baseline_BCVA Treatment/ties=exact;

run;

where CENSOR indicates censored subjects.

In all analyses, data from subject visits after receipt of rescue medication will be imputed using last observation prior to receiving rescue medication for continuous endpoints and will be imputed as failures for success/failure variables.

Additionally, a subset of the efficacy analyses will be performed by combining the initial phase subjects with the randomization phase subjects.

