15.5 Clinical Laboratory Data

The observed and change from baseline values of hematology and clinical chemistry parameters will be summarized, overall and by treatment group, at each visit with continuous descriptive statistics. Normal ranges will be used to determine the classifications. Values below the normal range will be classified as low normal, low panic, values above the normal range will be classified as high normal and high panic, and values within the normal range will be classified as normal. Analyses will also include shifts from baseline to each post-baseline visit using low normal, and high classifications.

Subject listings will be provided for hematology and clinical chemistry separately and will include a column to distinguish abnormal values.

16. Interim Analyses

An interim analysis may be conducted when the first 20 subjects enrolled in the randomized phase complete their Month 6 visit or discontinued the study. Safety, tolerability, and efficacy data will be reviewed during this interim analysis to assist in planning of future studies. A final analysis will be performed when all randomized subjects in each treatment group have completed the Month 6 visit.

17. Changes from Protocol-Stated Analyses

1. Comparison between treatment groups for CRT will be performed as specified in Section 12.2.
2. Two time to event analyses for CRT will be performed as specified in Section 12.2.
3. No analyses will be performed for CFT.
4. Discrete summary statistics for patient receiving rescue therapy will be removed.

18. References

Brookmeyer, R. and Crowley, J. (1982) A confidence interval for the median survival time. *Biometrics* 1982; 38: 29-41.

19. Revision History

Summary of Changes

Section #	Description of Change
List of Abbreviation	More abbreviation terms added
8.2.1	Missing/partial dates for AEs handling added
8.2.2	Missing/partial dates for concomitant medication handling added
8.3	Baseline definition updated
9	COVID-19 related discontinuation and protocol deviation added to subject disposition summary and COVID-19 related protocol deviation listing added
12	Implant residual assessment added
13.1	1. Boxplot of change from baseline in BCVA letter score for study eye added for subject groups with gain of ≥ 15 letters, ≥ 10 letters, and ≥ 5 letters 2. More details for the event of receiving rescue therapy added

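### SAP 13.1 names the log-rank test only for time to response, so the only formulation comparison its prose gives time to rescue is an ordinary Cox model, which has no finite estimate if one arm has no rescues

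*SAP*

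**What the plan says.** **Methods assigned in SAP 13.1.** Kaplan-Meier medians with 90% and 95% confidence intervals are planned for two events, 15-letter response and rescue. Two sentences on comparison follow:
- Log-rank: "The log rank statistic will be used to determine differences in time to achieve response between the two treatment groups".
- Cox: "Cox proportional hazards will also be used to analyze time to event, including baseline BCVA as a covariate".

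The first names response. The second names no event, so it takes in rescue. Protocol 9.6.2 had limited the optional Cox model to time to response.

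**Example code in SAP 13.1.** One LIFETEST block requests a log-rank test, and one PHREG block has the model line "model AVAL*CENSOR(0) = baseline_BCVA Treatment/ties=exact". Neither names an endpoint. The PHREG block requests no penalised likelihood, no profile-likelihood limits and no separate likelihood-ratio test of treatment.

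**Rescue as a proportion.** Protocol 9.6.2 compared rescue percentages by Fisher's exact test with Farrington-Manning intervals. SAP 17 item 4 says: "Discrete summary statistics for patient receiving rescue therapy will be removed". SAP 2.2 and SAP 13 still list the overall rescue percentage, with no comparison method. The only rescue table in SAP 20 is Table 14.2.3, time to rescue. SAP 1 states that the SAP's methods override the protocol's.

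**The concern.** Protocol 3.2 wants a formulation with a long duration of effect, and Month 6 data inform which formulation goes forward. Time to rescue bears directly on duration. Rescue can be sparse in arms of 20: it is offered for lack of efficacy after Month 3/Week 12, so events have about three months in which to accrue.

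An ordinary Cox model is a poor sole comparison for sparse events. If one arm has none, the partial likelihood keeps rising as the log hazard ratio moves towards infinity. The standard error becomes huge and the Wald test loses all information. A clear split would then come with an unusable hazard ratio and a Wald p-value near 1. The Kaplan-Meier median does not fill the gap, because it will usually not be reached if fewer than half of an arm is rescued.

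**Working it through.** **Inputs from the documents**
- Level (SAP 8.4): "All statistical tests will be two-sided with a significance level of 0.05".
- Arm size (SAP 5): "With a sample size of 20 evaluable subjects per treatment group".
- Allocation (SAP 4.1): "subjects will be assigned in a 1:1 ratio to either AR-1105-CF1 or AR-1105-CF2".
- Rescue rate: none given. SAP 5 says "This study is not powered to detect a pre-stated efficacy signal". All rescue risks below are assumptions, shown over a range.

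**The plan's own figure.** The zero-event bound in SAP 5 is 1 − 0.05^(1/20) = 0.139, which reproduces the stated 13.9%. By the same formula, an arm with 0/20 rescues is still compatible with a true risk up to 13.9%.

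**Worked case, 0/20 v 6/20.** Assume six distinct rescue times and nobody censored before the last of them. Just before event j (j = 0 to 5), 20 subjects are at risk in the empty arm and 20 − j in the other.

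*Log-rank.* Expected events in the empty arm are Σ 20/(40 − j) = 3.207. The variance is Σ 20(20 − j)/(40 − j)² = 1.489. Chi-square = 3.207²/1.489 = 6.90, p = 0.009.

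*Fisher.* 2 × C(20,6)/C(40,6) = 2 × 38,760/3,838,380 = 0.020.

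*Ordinary Cox, treatment only.* With β the log hazard ratio for the empty arm, the log partial likelihood is −Σ log(20e^β + 20 − j). It falls steadily as β rises, so its maximum is at β = −∞ and no finite estimate exists.

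*Likelihood ratio for treatment.* 2 log[C(40,6)/C(20,6)] = 2 log(99.03) = 9.19, p = 0.0024. The data are informative; it is the Wald test that fails.

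*Firth-penalised Cox, treatment only.* Hazard ratio 0.067, profile 95% interval 0.0005 to 0.56.

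**Other splits.** These are medians over 60 simulated data sets per row, 20 per arm, with baseline BCVA in the Cox model and Efron ties as an approximation to the exact method.

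| Rescues | Cox Wald p | Log-rank p | Treatment likelihood-ratio p | Fisher p |
|---|---|---|---|---|
| 0 v 4 | 0.997 | 0.037 | 0.015 | 0.106 |
| 0 v 5 | 0.996 | 0.018 | 0.0065 | 0.047 |
| 0 v 6 | 0.996 | 0.0086 | 0.0025 | 0.020 |
| 0 v 8 | 0.995 | 0.0017 | 0.0003 | 0.0033 |
| 0 v 10 | 0.995 | 0.0003 | 0.00004 | 0.0004 |

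From 0 v 2 up to 0 v 20, the fitted coefficient was about ±18 to 20 with a standard error of about 2,300 to 6,300. The Wald p stayed between 0.992 and 0.998, whichever arm was empty.

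**Chance that a given arm is empty, (1 − p)^20.** At p = 2%: 67%. At 5%: 36%. At 10%: 12%. At 20%: 1%.

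**Chance of p < 0.05.** Simulated with 20 per arm, rescues uniform over Months 3 to 6 and follow-up to Month 6. The log-rank column uses a permutation p-value when total events are 5 or fewer. Ranges reflect separate simulation runs.

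| True rescue risks | Log-rank | Cox Wald |
|---|---|---|
| 5% v 30% | 52-54% | 17% |
| 5% v 25% | 33-35% | 7-8% |
| 10% v 30% | 31% | 15% |
| 20% v 40% | 24-29% | 20-24% |
| 30% v 60% | 45-47% | 43-44% |

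The permutation step matters. For 0 v 4 the asymptotic log-rank p is 0.037, but the exact p is 2 × C(20,4)/C(40,4) = 2 × 4,845/91,390 = 0.106. With equal risks of 5%, 10% and 20%, even the asymptotic log-rank test rejected in only 1.4%, 4.2% and 5.1% of trials.

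**The case against.** **A log-rank test for rescue may be intended.** The LIFETEST code is endpoint-neutral and follows the definitions of both events, and the Cox model is described as an addition. Run on the rescue data, the code gives a valid log-rank p. This stands as far as it goes: the SAP permits that reading but does not state it. SAP 13.2 points to the method for the response event by name, so the document does tie methods to events. Whether rescue gets a log-rank test should not be settled after the data are seen. The Cox hazard ratio would still have no finite estimate.

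**Other summaries would show the split.** SAP 2.2 and 13 keep the overall rescue percentage, and Kaplan-Meier results appear in Table 14.2.3. A reader might infer from SAP 17 item 4 that rescue percentages are gone from the plan. The documents contradict each other on this, so that inference is not supported. What is gone is a comparison method for them.

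**Only the Wald p is near 1.** This is correct. The treatment likelihood-ratio p is 0.0025 at 0 v 6. However, with the code shown, PHREG's default likelihood-ratio and score tests are global and mix treatment with baseline BCVA. No treatment-only test is requested.

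**Rescue may be common.** This is also fair. The CRT and BCVA thresholds are minimum guidelines and the decision is the investigator's. Protocol 1 says the existing dexamethasone implant typically needs re-injection every 3 months. When both risks are 20% or more, the log-rank advantage nearly disappears.

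**The study is exploratory.** No p-value rule governs the choice of formulation. Implant visibility, loss of edema resolution, and monthly CRT and BCVA also bear on duration. This limits the consequence, but a usable estimate and interval for rescue still matter.

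**Conclusion.** The point holds as a gap in the prose with a conditional failure. As written, SAP 13.1 assigns time to rescue one comparison of the formulations, and it has no finite estimate when an arm has no rescues. The chance of that in a given arm of 20 is 36% at a true risk of 5%, 12% at 10% and 1% at 20%. It is therefore realistic only if one formulation's rescue risk is about 10% or less. In the simulated pairs of that kind, the Wald test had about a fifth to a half of the log-rank test's chance of p < 0.05 (7-8% v 33-35%, up to 15% v 31%). At 20% v 40% and above, the two are close.

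A reader might infer that a clear durability difference would necessarily be reported with p near 1. The documents do not support that: the generic LIFETEST code could give a log-rank p, the overall percentage is still listed, and the failure needs an empty arm. Nor do they support a claim that few rescues are expected, since they give no rate.

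The percentages rest on the assumed risks. The power figures also assume 20 evaluable subjects per arm, rescues uniform over Months 3 to 6, follow-up to Month 6 and, for the Cox model, a baseline covariate unrelated to rescue.

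**What to change.** 1. In SAP 13.1, extend the log-rank sentence to cover both time to response and time to rescue therapy. Make it the between-formulation test for rescue, with an exact permutation p-value when total rescues are 5 or fewer.
2. Fit the Cox model for rescue with Firth's penalised likelihood and report profile-likelihood limits, so that a hazard ratio and interval exist when an arm has no events.
3. Reconcile SAP 17 item 4 with SAP 2.2 and 13. State whether the overall rescue percentage is reported and, if it is, with what comparison.

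The cost is a few SAP sentences, an option in the PHREG code and a short permutation program. No new data are needed. The Firth estimate is shrunk slightly towards no difference. The permutation p-value is more conservative than the asymptotic one, as the 0 v 4 case shows.
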